### Exclusion Criteria

1. Active infection or wound complication at implant site.
2. Significant psychiatric comorbidity (e.g. uncontrolled depression, psychosis).
3. Planned surgery, stimulation adjustments, or medication changes within 2 weeks prior to enrolment or at any time during the study period.
4. Pregnancy or breastfeeding.
5. Occurrence of any adverse event during the study that meets the predefined withdrawal criteria (see Safety Monitoring); such participants are withdrawn immediately and not re-randomized.

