## Randomisation & Blinding Procedures

Randomization is generated automatically within the Patientkollen® patient-management platform using concealed permuted blocks (1:1 allocation) and stored entirely inside the single-site environment at Umeå University Hospital; no files are exported outside the platform.

To maintain blinding: After each treatment period, participants will be asked whether they experienced any paresthesia during the preceding stimulation phase, in order to assess whether the study was genuinely blinded. We will not ask participants to identify whether they believe the period involved sham or active stimulation, as such judgements could be influenced by perceived analgesic benefit. Prior to study initiation, a pre-trial acute detection test will be performed in 10 participants: each will undergo 10 randomized one-minute sessions (stimulator ON at 80% perception threshold or OFF), and after each session indicate whether or not paresthesia was perceived. This will ensure the feasibility of maintaining blinding in the main trial. The programming nurse makes all parameter changes while the participant's handheld programmer is hidden from view.

- After programming, the handheld unit is *locked* with a unique access code known only to the nurse and stored in the electronic Trial Master File (eTMF).
- In a documented emergency (e.g. device-related adverse event or intolerable pain), the code may be disclosed by an investigator uninvolved in outcome assessment. Disclosure automatically withdraws the participant from the study; the reason is logged in the eTMF.

Unblinding procedure: Once the final participant completes Day 10, Patientkollen runs automated integrity checks (range, consistency, missing-value rules) and locks the dataset. The platform then executes predefined statistical scripts comparing sequence labels A and B without human intervention. After the automated analysis is complete, the research team convenes, and the programming nurse activates the “reveal” function in Patientkollen to link each label to its actual treatment order. The validated dataset, analysis outputs, and audit trail then become accessible to the full study group.

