## Statistical Analysis Plan

- Sample Size – Assuming within-subject SD = 1.5 NRS points, minimally important difference = 1 point,  $\alpha = 0.05$ , power = 0.90, two-sided paired test → 24 completers needed (calculated with G\*Power). To accommodate 15 % attrition, target enrolment = 28.
- Primary Analysis – Paired t-test (or Wilcoxon signed-rank if non-normal) comparing mean NRS pain across days 3–5 between Active and Sham periods. If a period is aborted due to high pain, the last recorded score will be carried forward for the remaining days. Treatment order and carry-over tested via mixed-effects model with fixed effects for treatment, period, and sequence.
- Secondary Outcomes – Similar within-subject comparisons; Bonferroni correction applied.
- Missing Data – Multiple imputation if > 5 % diary fields missing.

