## Safety Monitoring

All adverse events (AEs) occurring between screening and study exit lead to the immediate withdrawal of the participant from the trial. If the AE is judged related to either the DRG stimulation or the sham condition, it is captured in the study database with these mandatory details: (i) AE type and MedDRA term, (ii) date/time of onset, (iii) action taken (e.g., device OFF, medical treatment), and (iv) final outcome/resolution.

The event report is recorded in Patientkollen within 24 h via the SAE portal and automatically forwarded to the Data Safety Monitoring Board (DSMB) for review at its next meeting.

**Intraperiod stopping rule:** If any diary entry records (i) an NRS pain score > 8 or (ii) an increase  $\geq 4$  points versus Baseline Day 0, the current treatment period is halted. The

participant immediately enters the 24 h wash-out and then crosses to the alternate arm. The episode is logged as an AE (device insufficient efficacy) and triggers a real-time alert to the DSMB.

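### Withdrawal for any adverse event contradicts the high-pain stopping rule and, read literally, loses pairs to minor unrelated events

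*Combined protocol and SAP*

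**What the plan says.** Safety Monitoring opens with a general rule: "All adverse events (AEs) occurring between screening and study exit lead to the immediate withdrawal of the participant from the trial". Relatedness enters only in the next sentence, and only for data capture: "If the AE is judged related to either the DRG stimulation or the sham condition, it is captured in the study database", with four mandatory details.

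The stopping rule in the same section applies when a diary score exceeds 8 or has risen by 4 points or more from Baseline Day 0. It halts the current period only. The "participant immediately enters the 24 h wash-out and then crosses to the alternate arm". It then adds: "The episode is logged as an AE (device insufficient efficacy) and triggers a real-time alert to the DSMB".

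The Statistical Analysis Plan provides for the same event: "If a period is aborted due to high pain, the last recorded score will be carried forward for the remaining days". The primary test is paired and compares mean pain over days 3–5 of the two periods.

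Exclusion criterion 5 withdraws participants on "Occurrence of any adverse event during the study that meets the predefined withdrawal criteria" and refers the reader to Safety Monitoring for them. Outcome Measures lists adverse events as a secondary outcome.

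**The concern.** A stopping-rule episode is, by the plan's own classification, an AE. The general rule withdraws that participant; the stopping rule keeps the participant in and moves them to the other condition. No exception is written. This is the event most closely tied to the primary outcome, so staff should not have to infer which rule applies.

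Two things are at stake:

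- **Selective loss.** If stimulation works, high-pain episodes should be commoner on sham. Withdrawing those participants would remove pairs likely to show a large sham-minus-active difference. The loss would then depend on the outcome and would not be only a loss of precision.
- **Needless loss.** With no filter for severity or relatedness, a cold or an unrelated headache during Period 1 ends participation and leaves nothing to pair.

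**Working it through.** **1. The plan's own figure.** Inputs from the Statistical Analysis Plan: SD 1.5, difference 1, two-sided α 0.05, power 0.90. The normal approximation gives n = ((1.960 + 1.282) × 1.5 / 1)² = 23.64, so 24, as stated. The exact noncentral-t calculation gives 26, and power at 24 pairs is 0.878. Enrolment of 28 agrees with 24 × 1.15 = 27.6. Taking 15 % off 28 leaves 23.8, so nothing is held in reserve beyond the planned attrition.

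**2. The rules side by side for a high-pain abort.**

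| Abort in | General AE sentence | Stopping rule | Carry-forward |
|---|---|---|---|
| Period 1 | Withdraw, so no Period 2 data | Wash-out, then the other condition | Fills Period 1; useful to the paired test only if Period 2 follows |
| Period 2 | Withdraw | No untried condition remains | Fills Period 2; Period 1 is already complete, so a pair can be formed |

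The conflict with carry-forward is therefore confined to Period 1. In Period 2 the rules can coexist, provided that at least one Period 2 score exists and a withdrawn participant's data are kept.

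**3. Which other AEs cost a pair.** Period 2 runs on Days 6–10, so its days 3–5 are Days 8–10. An AE on Days 0–7 (8 days) leaves no Period 2 data in the primary window. An AE on Days 8–10 may leave some. An AE before randomisation costs a recruit, not a randomised pair.

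**4. Illustrative size.** The documents give no AE rate. The daily rates r below are assumptions, taken as constant and independent between participants, and only AE losses are counted. The loss probability is q = 1 − (1 − r)⁸, the expected loss is 28q, and the chance of keeping at least 24 pairs is P(Bin(28, q) ≤ 4).

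| Assumed r per day | q | Expected loss of 28 | Chance of at least 24 pairs |
|---|---|---|---|
| 0.5 % | 3.9 % | 1.10 | 0.996 |
| 1 % | 7.7 % | 2.16 | 0.939 |
| 1.5 % | 11.4 % | 3.19 | 0.792 |
| 2 % | 14.9 % | 4.18 | 0.592 |

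The expected loss reaches the 4 that the plan allows for (28 − 24) at r = 1 − (24/28)^(1/8) = 1.91 % per day. If a completer must instead reach Day 10 (11 days, Days 0–10), the last column becomes 0.985, 0.837, 0.568 and 0.318.

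**5. Power.** With 1.5 read as the SD of the paired difference, noncentral-t power is 0.88 at 24 pairs, 0.85 at 22 and 0.81 at 20.

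**The case against.** The strongest reply is that a specific rule normally governs a general one. The stopping rule sets out a procedure, the carry-forward rule supports it, and a sensible team would cross the participant over. That stands as evidence of intent. It does not supply the missing exception, and it does nothing for ordinary unrelated AEs, where only the general sentence speaks. The selective-loss argument is also conditional: it needs staff to follow the general sentence, stimulation to work, and episodes to cluster on sham.

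Withdrawing everyone who has an AE could be a deliberately cautious choice in a short elective study. The protocol gives no such rationale, and the reference in exclusion criterion 5 to set criteria suggests that something narrower was meant.

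The pair may not be wholly lost. Multiple imputation is planned once more than 5 % of diary entries are missing, and the mixed model could use single-period data. But the plan does not say that imputation covers withdrawn participants, and it specifies the model for order and carry-over, not as the primary test.

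A reader might see a further contradiction in the emergency clause under Randomisation & Blinding Procedures: "In a documented emergency (e.g. device-related adverse event or intolerable pain), the code may be disclosed by an investigator uninvolved in outcome assessment", after which "Disclosure automatically withdraws the participant from the study; the reason is logged in the eTMF". The documents do not support that. Disclosure is optional and kept for emergencies, and the programming nurse, who already knows the code, makes all parameter changes. A stopping-rule crossover therefore needs no disclosure.

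**Conclusion.** The opening sentence of Safety Monitoring is wrong as written. It contradicts the stopping rule below it, makes carry-forward useless to the paired test for a Period 1 abort, and withdraws participants for events unrelated to treatment. This holds at any AE rate.

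The size of the loss is unknown. Under the assumed rates it runs from negligible to about the whole attrition allowance, and the effect on power is modest. The power figures also rest on reading the stated SD as that of the paired difference.

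Three stronger inferences are not supported:

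- **That the rule leaves the trial underpowered.** Every rate behind the loss figures is assumed.
- **That AEs go uncollected after withdrawal.** The documents are silent on follow-up of withdrawn participants.
- **That exclusion criterion 5 gives an opposite instruction.** Its qualifier is merely emptied, because the section it refers to sets no criterion narrower than all AEs.

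This should be fixed before enrolment, but it is not fatal to the design.

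**What to change.** 1. In Safety Monitoring, replace the first sentence with a short list of AEs that require withdrawal, for example serious events, or device-related events that make continuing unsafe. State that participants with any other AE continue.
2. State there that stopping-rule episodes are logged as AEs, follow the crossover rule and are not withdrawals.
3. Let exclusion criterion 5 point to that list.
4. As a separate matter of recording, capture the four listed details (type and coded term, onset, action, outcome) for every AE and not only those judged related, since AEs are a secondary outcome.

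The sample size and primary test do not change. The cost is a wording change in two sections, slightly more AE recording, and possibly an ethics amendment, since approval is already held.

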## Purpose and Aims

DRG stimulation is today considered a standard therapy for several neuropathic pain conditions. Despite its widespread clinical use, a critical knowledge gap remains: the efficacy of DRG stimulation has never been validated against sham in a controlled trial. The only randomized controlled study conducted to date is an industry-sponsored comparison between DRG stimulation and spinal cord stimulation (SCS) (9), but no trial has directly tested DRG against placebo.

Umeå University Hospital is internationally recognized as a leading center for DRG stimulation. Patients from across Sweden are referred to our department, making our clinic the de facto national referral center for this therapy. In practice, DRG therapy is centralized to our unit. The resulting high patient volumes, together with our long-standing expertise and comprehensive quality database, provide unique opportunities to fill this knowledge gap—opportunities that no other center is currently positioned to offer.

The purpose of this study is therefore to rigorously evaluate whether ongoing sub-threshold DRG stimulation provides genuine analgesic benefit beyond contextual or placebo effects. Sub-threshold programming is already the accepted standard within DRG stimulation, but the specific contribution of this approach remains to be clarified in a placebo-controlled setting. Addressing this knowledge gap will provide robust scientific evidence to support or refute the physiological efficacy of sub-threshold DRG stimulation.

Our primary aim is to determine the impact of sub-threshold DRG stimulation on pain intensity in established responders, using a double-blind, crossover design. Secondary aims include assessing effects on sleep, mood, and activity, as well as evaluating the feasibility of maintaining blinding and capturing safety and tolerability data.

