## Objectives & Hypotheses

- Primary Objective – To compare mean daily pain intensity during five days of sub-threshold DRG stimulation versus sham.
- Secondary Objectives – To compare sleep quality, mood, and daily activity between conditions; to assess safety and tolerability; to explore within-subject carry-over effects.
- Primary Hypothesis – Sub-threshold DRG stimulation will reduce mean Numeric Rating Scale (NRS, 0–10) pain scores compared with sham.

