## Study Schedule & Assessments

Study Day	Activity
-7 to -1	Screening, informed consent, baseline questionnaires, recording perception threshold.
0	Randomization; begin first 24 h wash-out (device OFF).
1-5	Period 1 treatment (Active or Sham) + twice-daily electronic diary.
5	24 h wash-out (device OFF).
6-10	Period 2 treatment + diaries.
10	End-of-study visit, adverse event review, exit interview

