## Outcome Measures

Category	Measure	Time-Points
Primary	Average NRS pain (0–10) across 5 treatment days	Daily AM & PM
Secondary	Sleep quality (5-point PGIC)*	Daily AM
	Mood (5-point PGIC)*	Daily PM
	Daily activity (5-point PGIC)*	Daily PM
	Adverse events	Continuous
Exploratory	Device usage logs, rescue medication use	Daily

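### Safety Monitoring ties database capture of an adverse event to a relatedness judgement, while the objectives and outcome table make adverse events an unrestricted secondary outcome

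*Combined protocol and SAP*

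**What the plan says.** All references are to the combined protocol and SAP.

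- **Safety Monitoring, capture.** "If the AE is judged related to either the DRG stimulation or the sham condition, it is captured in the study database". The mandatory details are what the event was (coded in MedDRA), when it began, what was done, and how it ended.
- **Safety Monitoring, routing.** The next paragraph adds: "The event report is recorded in Patientkollen within 24 h via the SAE portal", with automatic forwarding to the DSMB.
- **Safety Monitoring, withdrawal.** The section opens with: "All adverse events (AEs) occurring between screening and study exit lead to the immediate withdrawal of the participant from the trial".
- **Safety Monitoring, stopping rule.** A period halted for high pain is followed by wash-out and the other arm. "The episode is logged as an AE (device insufficient efficacy) and triggers a real-time alert to the DSMB".
- **Outcome Measures.** "Adverse events" stands under the secondary outcomes, collected continuously, with no restriction to related events.
- **Objectives & Hypotheses** and **Purpose and Aims.** A secondary objective is "to assess safety and tolerability"; a secondary aim includes "capturing safety and tolerability data".
- **Study Schedule & Assessments, Day 10.** "End-of-study visit, adverse event review, exit interview", with no rule on which events are entered.
- **Exclusion Criteria, item 5.** Withdrawal follows an adverse event that meets predefined withdrawal criteria, with a reference to Safety Monitoring.
- **Statistical Analysis Plan.** Secondary outcomes get within-subject comparisons like the primary one, with Bonferroni correction. No adverse-event summary is described.

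**The concern.** The outcome and the rule that feeds it do not match. The outcome is all adverse events; the only general recording rule in the plan starts from a judgement of relatedness. Whether an event is caused by stimulation, or by its absence, is part of what the Active versus Sham safety comparison should help to answer. Here that judgement helps to decide what enters the data. The plan does not say who makes it, by what criteria, or whether that person is blinded.

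A judgement stored as a field can be revisited at analysis. An event that was never entered cannot. If unrelated events go unrecorded, the trial can report related events by condition but not the adverse-event outcome it lists. Under the opening sentence of Safety Monitoring, a participant could also leave the trial because of an unrelated event without any adverse-event entry to explain it. With 28 participants planned, each such event counts.

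**Working it through.** The point is textual, and no design figure in the plan bears on it. The check is whether any section supplies the record that the capture sentence leaves out.

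1. **Capture sentence.** Judged related: capture with four details is required. Judged unrelated: the sentence is silent.
2. **Event report.** This sentence follows directly on the one about related events and names no separate route for others. At most it is unclear whether unrelated events reach the platform and the DSMB.
3. **Stopping-rule episodes.** These are logged as adverse events with no stated relatedness step. They are labelled as insufficient efficacy of the device, so they do not show that unrelated events are recorded.
4. **Day 10 review.** An activity is scheduled, without a recording rule.
5. **Audit log (Data Collection & Management).** Actions taken in the platform are time-stamped. That does not oblige anyone to enter an unrelated event.
6. **Reason logged in the eTMF (Randomisation & Blinding Procedures).** This applies only when the access code is disclosed in an emergency.

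No section requires entry of an event judged unrelated, whereas Outcome Measures and the objectives set no such limit.

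**Withdrawal statements side by side.**

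| Place | Consequence of an adverse event |
|---|---|
| Safety Monitoring, opening sentence | Any event: immediate withdrawal |
| Exclusion Criteria, item 5 | Withdrawal if predefined criteria are met |
| Safety Monitoring, stopping rule | Episode is logged as an adverse event; participant crosses to the other arm |

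These three cannot all hold. How often an unrelated event would end participation therefore depends on which one is followed.

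**Scale, by assumption only.** Suppose 0.1 to 0.3 adverse events per participant and a related share of 25% to 75%. Neither range comes from the documents. With the planned enrolment of 28:

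- expected events: 28 × 0.1 = 2.8 to 28 × 0.3 = 8.4;
- fewest unrelated: 2.8 × (1 − 0.75) = 0.7;
- most unrelated: 8.4 × (1 − 0.25) = 6.3.

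That is roughly 1 to 6 events for which no entry is required, out of about 3 to 8. The conclusion does not rest on these numbers.

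**Period and condition without a form field.** Date and time of onset is already a mandatory detail, and the audit log time-stamps parameter changes. After the reveal, each event can be placed in screening, wash-out, Period 1 or Period 2. The time matters as well as the date: the schedule puts both treatment and a wash-out on Day 5, and a halted period shifts the later boundaries.

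**The case against.** The strongest reply is that the capture sentence does not contain the word only. It gives a sufficient condition, and can be read as setting the level of detail for related events while others are recorded more simply. The unfiltered outcome listing, the Day 10 review and the logging of stopping-rule episodes all fit that reading. This stands in part: a reader might infer that the plan forbids or excludes recording of unrelated events, and it does not say so. But on the milder reading there is still no rule that unrelated events be entered, so the same correction is needed.

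Three further replies stand.

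- **Withdrawal.** A reader might take it as settled that every adverse event removes the participant. Exclusion criterion 5 and the stopping rule contradict that, so an unexplained withdrawal is a possibility under one of the conflicting statements and not a certain result.
- **Primary analysis.** A reader might infer that the filter damages the primary comparison or its missing-data handling. Nothing in the Statistical Analysis Plan uses relatedness or the reason for an adverse event. Imputation depends on the share of missing diary fields, and carry-forward on a period aborted for high pain; high-pain halts under the stopping rule are logged in any case. Any effect would be indirect, through poorly explained missing data.
- **Direction.** Participant, treating clinician and outcome assessors are blinded. If one of those roles judges relatedness, there is no evident reason for the loss to favour one condition. The documents support incomplete data, not a bias in a known direction.

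**Conclusion.** The point holds as a mismatch between an unrestricted secondary outcome and a recording rule conditional on causality, with no other section filling the gap. It should be fixed; it is not a threat to the trial's main result. What is at stake is completeness of the safety data and the ability to reclassify events later. It rests on two readings: that staff follow the written rule, and that silence on unrelated events means entry is not required. The documents give no figure for the share of events affected, so none is claimed. The three withdrawal statements are a separate contradiction that the sponsor must resolve; this review takes no position on which should stand.

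**What to change.** 1. **Safety Monitoring.** Reword the capture sentence so that every adverse event from screening to study exit is entered with the four details already listed. Make relatedness a field completed by a named, blinded role, not a condition for entry. State whether the event report and DSMB forwarding cover all events.
2. **Period and condition.** Derive both from onset date and time after the reveal. Do not put condition on the form: allocation is visible only to the programming nurse until then, reports go automatically to the DSMB, and screening events have no condition to enter.
3. **Statistical Analysis Plan.** Add a descriptive summary of all adverse events and of related adverse events by condition, with screening and wash-out events shown separately.
4. **Consistency.** Reconcile exclusion criterion 5, the opening sentence of Safety Monitoring and the stopping rule on what follows an adverse event.

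The cost is a few sentences, one extra field in an existing portal, and a small amount of extra data entry. Items 1 to 3 change no treatment, visit or sample size.

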## Study Design

- Randomized, double-blind, two-period crossover.
- Two treatment arms of 5 days each, separated by a 24 h wash-out.
- Order of conditions (Active → Sham or Sham → Active) allocated 1:1 using computer-generated random blocks.
- Participant, treating clinician, and outcome assessors blinded.

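### Safety Monitoring requires a participant who meets the pain stopping rule to be both withdrawn and crossed to the other arm

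*Combined protocol and SAP*

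**What the plan says.** Safety Monitoring contains three statements that bear on one event.

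- A general rule: "All adverse events (AEs) occurring between screening and study exit lead to the immediate withdrawal of the participant from the trial".
- The intraperiod stopping rule. A diary entry with NRS above 8, or at least 4 points above Baseline Day 0, halts the period, and the "participant immediately enters the 24 h wash-out and then crosses to the alternate arm".
- A classification of that halt: "The episode is logged as an AE (device insufficient efficacy"), with a real-time alert to the DSMB.

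Three other sections touch the same event.

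- Exclusion Criteria, item 5, withdraws participants on "Occurrence of any adverse event during the study that meets the predefined withdrawal criteria (see Safety Monitoring").
- Statistical Analysis Plan, Primary Analysis: "If a period is aborted due to high pain, the last recorded score will be carried forward for the remaining days".
- Randomisation & Blinding Procedures allows the access code to be disclosed in an emergency, with intolerable pain as one example, and withdraws the participant automatically when that happens.

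Study Design describes the trial as "Randomized, double-blind, two-period crossover". The primary analysis is a paired t-test, or a signed-rank test, on the Active and Sham means over days 3–5.

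**The concern.** A stopping-rule halt is an adverse event by the protocol's own classification, and every adverse event means withdrawal. The same paragraph keeps the participant in the trial and moves them to the other condition. Staff who act on a halt alert have two instructions and no order of precedence, so the same event could be handled differently from one participant to the next.

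The choice also decides who is in the primary analysis. A participant who crosses supplies a pair. A participant withdrawn after a Period 1 halt does not. Such losses are not random, because high recorded pain selects them. Halts are foreseeable here: participants are established responders, sham is the device switched off, and a single diary entry can trigger the rule. The analysis scripts run automatically after database lock, so the described process has no step at which inconsistent handling could be sorted out before results appear.

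**Working it through.** **1. One event under each rule.** Take a participant in Period 1 who records an NRS of 9.

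| Rule | Consequence |
|---|---|
| Stopping rule | Period halted, 24 h wash-out, then the other condition |
| Classification in the same rule | The halt is an adverse event |
| General adverse-event rule | Immediate withdrawal from the trial |

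The first and third rows exclude each other, and the second brings the event under the third.

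**2. Does another section settle it?**

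- Exclusion criterion 5 implies that only some adverse events lead to withdrawal, but it takes its criteria from Safety Monitoring. The only adverse-event withdrawal criterion there is the all-events sentence, so the reference returns to the conflict.
- The carry-forward rule fills the rest of a period aborted for pain. That is useful mainly if the participant stays in the analysis, so it points to crossing.
- The code-disclosure clause gives device-related adverse events as an example and attaches withdrawal to the disclosure. If every adverse event already meant withdrawal, the clause would be largely redundant for those events. This also points to crossing.
- None of these states precedence. Crossing is the probable intent, by inference.

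**3. What the withdrawal sentence would do to the analysis.** A Period 1 halt followed by withdrawal leaves no Period 2 record.

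- Carry-forward fills only the aborted period.
- The mixed-effects model is named for order and carry-over, not as the primary analysis.
- The imputation rule, "Multiple imputation if > 5 % diary fields missing", does not say whether the share is counted per participant or across the trial. Whether it would start after one withdrawal cannot be determined.

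The participant therefore has no clearly defined route back into the paired test.

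**4. Numbers of pairs.** Inputs from Sample Size: difference 1 point, SD 1.5 (taken as the SD of the paired differences), two-sided 0.05, power 0.90.

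- Plan's figure: n = [1.5 × (1.960 + 1.282) / 1]² = 23.64, rounded up to 24. This reproduces the stated 24 completers.
- Enrolment: "To accommodate 15 % attrition, target enrolment = 28"; 24 × 1.15 = 27.6, rounded up to 28. The margin is 28 − 24 = 4 participants for all causes of loss.
- Exact paired-t power: 0.925 at 28 pairs, 0.878 at 24, 0.863 at 23, 0.846 at 22, 0.807 at 20.

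One further lost pair below 24 costs 0.878 − 0.863 = 0.015 of power. Loss of numbers alone is a modest issue unless halts are frequent.

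**5. Direction of the selection effect.** Let D be the mean Sham-minus-Active difference over all N participants, and let k lost pairs have mean difference d. The retained mean is

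(N·D − k·d) / (N − k) = D − k·(d − D) / (N − k).

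The estimate falls below D only if d exceeds D. That is expected if Period 1 halts occur mainly on sham, because the lost pairs then come from the Sham-first sequence and tend to have high sham pain. If halts are equally common in both conditions, no such shift would be expected. The documents give neither k nor d, so no value can be attached.

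**The case against.** The strongest reply is that the documents already lean to one answer. The stopping rule is the specific instruction, carry-forward presumes continued participation, criterion 5 implies that not every adverse event means withdrawal, and code disclosure has its own withdrawal route. A sensible investigator would cross the participant, and any harm arises only on the less likely reading. The account of intent stands. It does not remove the conflict, because the general rule covers all adverse events, the halt is expressly classed as one, and no precedence is stated.

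A reader might also infer more than the text supports.

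- *A stated loss of power or a stated bias.* The documents give no halt rate and no differences for halted participants. A scenario with halts spread over all 28 participants and one with halts concentrated on sham, where only about 14 are exposed in Period 1, are different scenarios. Their results cannot be combined into one headline figure.
- *That the pairs lost are those with the largest Sham-minus-Active difference.* The trigger is a single high entry or a rise from Day 0. A participant with high habitual pain can meet it in a flare without a large difference between conditions.
- *That imputation would stay inactive after a few withdrawals.* With no stated denominator, this cannot be said either way.
- *That a Period 2 halt calls for a third period.* The crossing instruction is not limited to Period 1, but in a two-period design with an exit visit on Day 10 it can sensibly apply only there. This is a minor missing detail.

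**Conclusion.** The text is wrong as written: Safety Monitoring orders withdrawal and continuation for the same event, and no other section resolves it. Crossing is probably what the sponsor means.

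If the withdrawal sentence is followed, each Period 1 halt removes one pair from the primary test, from a planned margin of 4. The power cost per pair is small. The selection matters more: on the assumption that halts are commoner on sham, the estimate would be pulled toward no effect, by an amount the documents cannot fix. The contradiction itself rests on no assumption. The power figures rest on reading 1.5 as the SD of the paired differences.

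**What to change.** Make four short changes, preferably before the first participant is enrolled.

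1. **Safety Monitoring, withdrawal.** Exempt stopping-rule halts from the adverse-event withdrawal sentence. Replace the all-events wording with stated criteria for withdrawal, so that exclusion criterion 5 has something to refer to.
2. **Safety Monitoring, after a halt.** State that a Period 1 halt leads to the 24 h wash-out and then the other condition, and that a Period 2 halt ends study treatment.
3. **Statistical Analysis Plan.** State that halted participants stay in the paired analysis under the existing carry-forward rule. This takes that rule as given.
4. **Randomisation & Blinding Procedures.** State that a stopping-rule halt is handled without disclosing the code, so that intolerable pain leads to automatic withdrawal only if the code is actually disclosed. This is workable, because the programming nurse already holds the code and makes all parameter changes.

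The cost is a few sentences by protocol amendment, with no added patients, visits or procedures.
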